21.0 DATA SAFETY MONITORING BOARD

A Data Safety Monitoring Board (DSMB) will be selected to review the study conduct, feasibility data, and safety data and will review all types of adverse events reported in this study and adjudicate as required. The independent DSMB shall have the final adjudication for the events. A data safety charter will be established and will be approved by the DSMB. Qualifications for the DSMB members, at a minimum, shall include current experience with catheter directed thrombolysis for the treatment of submassive pulmonary emboli, management of the patient post-treatment and extensive research experience. Adherence to the study stopping criteria in this protocol will also be included in the DSMB meetings in addition to following the charter.

The DSMB shall have CEC responsibilities as well. This hybrid committee include CEC responsibilities that include providing an independent expert review of data on clinical events based on protocol-specific definitions. The CEC review ensures that events critical to the analysis of study results are assessed in a uniform manner. This facilitates reliable pooling of data within a trial and with predicate trials and improves the validity of comparisons with published data. In addition to study endpoints, the CEC will provide assessment of other events or areas of concern at the request of the DSMB or Sponsor (e.g., device malfunction or failure, serious anticipated adverse events versus serious unanticipated adverse events). Member selection will be based on:

- Balanced composition;
- Relevant expertise;
- Complete independence from the Sponsor and conduct of the trial;
- Evaluation and documentation of any Conflict of Interest; and
- Commitment to flexible schedules for the duration of the project life cycle.

22.0 STUDY STOPPING RULES

22.1 General Study Stopping Rules

The Sponsor, DSMB, IRBs, regulatory authorities, or the principal investigators may make recommendations to terminate the study if the safety and well-being of the subjects are in jeopardy.

If the study is terminated or suspended, prompt notification will be provided to all parties involved in the conduct of the study.

Patient enrollment may be paused or terminated early if the Sponsor or DSMB, and/or CEC determines that the potential benefits of the investigational device are unlikely to outweigh the risks associated with continuation of the trial.

22.2 Study Stopping Rules Related to Safety

22.2.1 Intracranial Hemorrhage

If three (3) patients undergoing the investigational procedure experience an unprovoked intracranial hemorrhage, confirmed by independent CEC/DSMB adjudication, and did not have a protocol violation such that he/she cannot be considered as representative of the intended patient population, the study shall be paused for re-evaluation, and may be stopped.

22.2.2 Bleeding

Should severe bleeding occur in 12 study subjects, the study will be paused, and the pharmacotherapy dosage and administration will be re-evaluated.

22.2.3 Ad Hoc Criteria for CEC/DSMB Meetings

1. If there are two (2) intracranial bleeds or eight (8) major bleeds within the first 60 subjects, an ad hoc meeting will occur for adjudication of the events.
2. An ad hoc meeting will take place if any untoward event that, in the opinion of the chair, warrants an ad-hoc meeting.

22.3 Device Study Stopping Rules

22.3.1 Device Related SAEs

Should it be suspected that a device caused a serious adverse event, the serious adverse event will be adjudicated by the independent DSMB and the device shall be returned to the manufacturer. A root cause analysis shall be performed. The DSMB will determine if the study should be stopped, temporarily suspended, or continued after each such event.

22.3.2 Device Malfunctions and Non-conformances

There are device malfunctions, or non-conformances, that may impact the patient and prevent treatment with an investigational device. Upon commencement of enrollment, if there are device failures that prevent a total of five (5) subjects across two or more study sites (e.g. site 01 has three (3) device malfunctions, and site 05 has two (2) device malfunctions) from being treated in this study, the study shall be paused for re-evaluation of the device. A root cause analysis will be performed to determine the cause(s) of the device failures and a corrective and preventative action will be implemented.

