6.4 Study Duration

6.4.1 Enrollment

It is estimated that up to 20 sites will be qualified to participate; they will enroll and treat up to 125 subjects (to achieve 100 evaluable subjects) over an estimate of 24 months. There may be an unlimited number of subjects consented for this study to achieve completion of 100 evaluable subjects. A maximum of 125 subjects will be enrolled, treated, and complete the study through 30-day follow-up. The subjects enrolled and treated per site will not exceed 20 subjects.

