20.3 Analysis Populations

All enrolled subjects who receive the study treatment will be included in the Intent-to-Treat (ITT) population. The ITT will consist of subjects who both provide informed consent to participate and have the BEC (or first of two BECs for bilateral PE) introduced into the sheath. The modified ITT (mITT) population are evaluable subjects defined as members of the ITT who have data available to assess the primary efficacy endpoint of reduction in RV/LV ratio as measured by contrast-enhanced chest CT (CTA) at screening and RV/LV ratio as measured by contrast-enhanced CTA at 48 hours after completion of r-tPA treatment. The patients comprising the mITT population are evaluable patients. Members of the ITT population who remain in the study long enough to complete the 30-day follow-up period will comprise the Per-Protocol (PP) population.

The mITT population will be used to analyze the primary efficacy endpoint. The ITT population will be used to analyze the primary safety endpoint, as well as all secondary safety and device endpoints that do not require 30 days of follow-up (e.g., device success, clinically relevant non-major bleeding, technical procedural complications). The PP population will be used to analyze secondary endpoints that require 30 days of follow-up: all-cause mortality, SAEs, AEs, UADEs, and recurrent PE through 30-day follow-up).

Up to 125 subjects, in up to 20 sites, will be enrolled and treated, with the objective to have at least 100 subjects complete the 30-day follow-up period, and be included in the primary efficacy analysis. Each site will have an enrollment cap such that no more than 20% (n=20) of participants are enrolled at a single site.

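### The device-failure pause in 22.3.2 needs failures at two or more sites, so a cluster confined to one site never triggers it automatically, whatever its size

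*Combined protocol and SAP*

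**What the plan says.** Section 22.3.2 is the only numeric rule for device failures. It applies to "device failures that prevent a total of five (5) subjects across two or more study sites" "from being treated in this study, the study shall be paused for re-evaluation of the device". A root-cause analysis and a corrective and preventive action follow. Its worked example reads "e.g. site 01 has three (3) device malfunctions, and site 05 has two (2) device malfunctions".

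Other parts of the protocol bear on device failures:

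- **22.3.1** starts with "Should it be suspected that a device caused a serious adverse event". Each such event, at any site, goes to the DSMB, with device return, a root-cause analysis and a decision to stop, suspend or continue.
- **21.0** has the CEC assess other matters "at the request of the DSMB or Sponsor (e.g., device malfunction or failure" among the examples).
- **22.1** allows the sponsor, DSMB and/or CEC to pause enrollment on benefit-risk grounds.
- **22.2.3**, item 2, lets the chair call an ad hoc meeting over an untoward event.

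Section 22.3.2 does not define 'treated'. Section 20.3 places a consented subject in the ITT population, described as those receiving study treatment, once they "have the BEC (or first of two BECs for bilateral PE) introduced into the sheath". The Device Success endpoint (6.2.3, item 1) speaks instead of therapy delivered without a device failure, and it counts devices.

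**The concern.** A count-based pause should respond at least as readily to a stronger signal as to a weaker one. This rule does not: the same five prevented subjects count when one of them is at a second site and do not count when all are at one site. Concentration at one site is a pattern that could reflect a problem with a batch, with handling or with operators, and a root-cause analysis is how these would be told apart. The plan gives no reason for the two-site condition.

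More than the pause is at stake. Under 22.3.2 the root-cause analysis and corrective action follow from the trigger. Under 22.3.1 device return and root-cause analysis require a suspected device-caused serious adverse event. A single-site cluster without such an event makes none of these steps mandatory.

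**Working it through.** **The rule as written.** Let T be the number of subjects whom device failures prevent from being treated, and S the number of sites with at least one such subject. The pause is mandatory if T ≥ 5 and S ≥ 2. The plan states no failure rate and no trigger probability, so the only figure to reproduce is its example: 3 + 2 = 5 at two sites, which fires.

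| Prevented subjects by site | T | S | Mandatory pause |
|---|---|---|---|
| 3 + 2 | 5 | 2 | yes |
| 4 + 1 | 5 | 2 | yes |
| 19 + 1 | 20 | 2 | yes |
| 5 at one site | 5 | 1 | no |
| 20 at one site | 20 | 1 | no |
| none prevented, any number of other malfunctions | 0 | 0 | no |

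**When the site condition matters.** Section 6.4.1 says of the sites that "they will enroll and treat up to 125 subjects" and adds: "The subjects enrolled and treated per site will not exceed 20 subjects". At least 125/20 = 6.25, so 7, sites are needed to reach the maximum, and up to 20 may take part. If failures fall evenly and independently over k sites, the probability that the first five are all at one site is k × (1/k)⁵ = 1/k⁴:

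- k = 7: 1/2,401 = 0.0004
- k = 10: 1/10,000 = 0.0001
- k = 20: 1/160,000 = 0.000006

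Without clustering, then, the condition almost never changes the outcome.

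**When failures cluster.** Assume 20 attempts at one site, a treatment-preventing failure rate q there, and no failures elsewhere. Both the rate and the number of attempts are assumptions. With X ~ Binomial(20, q):

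- q = 10%: P(X ≥ 5) = 0.04
- q = 25%: P(X ≥ 5) = 0.59
- q = 50%: P(X ≥ 5) = 0.99

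In all three cases the probability that 22.3.2 fires is 0, because S = 1.

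**What 'treated' means.** If it means that the catheter has entered the sheath, as in 20.3, a failure after that point leaves the subject treated and uncounted. If it means therapy delivered, as in Device Success, an in-body failure that blocks delivery counts. Section 22.3.2 does not choose. On either reading, a malfunction that does not prevent treatment adds nothing to T.

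**Subjects or malfunctions.** The rule counts subjects; its example counts malfunctions. A bilateral case uses two catheters, so two malfunctions may be one subject.

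**The case against.** The strongest reply is that serious failures are already covered, and more strictly. Under 22.3.1 a single suspected device-caused serious adverse event at any site brings DSMB adjudication and a decision on the study. The definition in 17.1 is broad and includes intervention needed to prevent permanent impairment. The discretionary routes in 21.0, 22.1 and 22.2.3 also exist, expansion, collapse and flow are checked before insertion (9.4, step 2), and one failure at a second site is enough to meet the site condition.

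All of this stands, and it limits the point. A reader might infer that a single-site cluster could not lead to a pause. The documents do not support that; what is missing is an automatic pause. A reader might also infer that failures inside the body never count. Section 22.3.2 excludes failures that do not prevent treatment and says nothing about where a failure occurs. A basket that cannot be deployed may prevent treatment and so count. It is excluded for certain only if the ITT wording is carried into 22.3.2, which the text does not do.

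It is also tempting to count every malfunction against the same five. That is a debatable trade-off: at an assumed, harmless malfunction rate of 4% in 125 subjects, P(at least 5) = 0.56, and at 10% it is 0.996.

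None of this justifies the two-site condition. The remaining routes depend either on harm or on someone choosing to act.

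**Conclusion.** The point holds as a gap in the automatic trigger. On the literal text, no number of treatment-preventing failures confined to one site makes the pause or the root-cause analysis mandatory, while 4 + 1 does. This rests on the wording alone and needs no assumed rate; the probabilities above only illustrate when it would matter.

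A second, narrower gap is that malfunctions in subjects who are still treated, without a serious adverse event, have no automatic trigger. How wide that gap is depends on the undefined word 'treated'.

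Removing the site condition is a worthwhile, low-cost improvement. The documents do not show that a cluster has been or would be missed, and they do not describe how device batches are distributed to sites.

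**What to change.** Delete the two-site condition from 22.3.2, so that five treatment-prevented subjects in total, at any number of sites, trigger the pause and the root-cause analysis. Adapt the example to match. Have the root-cause analysis use the batch numbers that investigators must already record (18.1, item 9) and the device log (19.2) to separate a lot problem from an operator problem.

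In the same edit:

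- define 'treated' for this rule and reconcile it with 20.3 and with Device Success;
- state whether subjects or malfunctions are counted, including when two catheters are used in one subject.

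Whether malfunctions in treated subjects should trigger review, and at what number, is for the sponsor and DSMB to decide.

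The cost is a short text amendment with no new data collection. The downside is that an operator-related cluster at one site may cause a short pause, which review can lift. When failures are spread over sites, the change has almost no effect.

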23.0 VERSION CONTROL

Add to table below for each protocol amendment

PROTOCOL THRO-CLIN-2019-01		
VERSION	SUMMARY OF THE CHANGE	RATIONALE
0.0	
Original for FDA Review
 
Edited per FDA request to add in the following sentence: enrollment will not be stopped at the interim analysis of n=60 patients and full enrollment is planned for the study.
	N/A
1.0	
Edited per FDA request to add in the following sentence: enrollment will not be stopped at the interim analysis of n=60 patients and full enrollment is planned for the study. [The rev number of this protocol reverts to the draft revision numbering in case there are additional changes to be made per FDA request. The final version approved by FDA will be changed to 1.0 once all final FDA requested changes are made and the IDE approval letter is received.]
	Make FDA requested changes and additional editorial changes.
2.0	
Enrollment capped at 20% of sample size per FDA request, statistical changes made per FDA IDE approval letter February 6, 2020, and administrative changes.
	
Implement changes in protocol according to recommendations in FDA IDE approval letter dated February 6, 2020.
 
Administrative changes were done to add clarification.

3.0	
Protocol amendment due to COVID-19, patient follow-up plan and Impact Assessment Form. Revise AE relatedness definitions and separate evaluation of device/drug from procedure events. Address FDA recommendations in IDE approval letter for S001 dated April 2, 2020.
	
New FDA Guidance on the conduct of clinical trials of medical products during the COVID-19 pandemic; capture more detail related to AE relatedness.

4.0	
The protocol was amended after the CEC/DSMB kick-off meeting. The CEC/DSMB members asked for guidance from the steering committee to change the study stopping rules from percentages to patient numbers and to add ad hoc criteria for when the CEC/DSMB chairperson would call an ad hoc meeting.
	
CEC/DSMB first meeting required changes to the stopping rules, criteria for ad hoc meetings, and to include emphasis on not cannulating arterial branches with the BEC at any time, add COVID-19 exclusion, and administrative changes were made.

25.0 APPENDICES

APPENDIX 25.1 REQUIRED STUDY PROCEDURES

Test	Pre-Procedure	Procedure	Post-Procedure	End of r-tPA Infusion	24 Hrs Post-r-tPA Completed	48 Hrs Post- r-tPA Completed	72 Hrs Post- r-tPA Initiated	Before Discharge	30-day Follow-up
Visit Window	≤ 48 Hrs of procedure				±8 Hrs	±8 Hrs	-4 / +12 Hrs	-8 Hrs	±7 Days
Informed Consent	X								
Demographics and Medical History	X								
Physical Examination	X			X	X			X	X ⁷
12 Lead ECG	X								
CBC, INR ¹	X				X				
aPTT	X ²		X	X					
CMP	X								
BMP					X				
Cardiac Biomarkers: Troponin, BNP	X				X				
Lower Extremity Venous DUS	X								
Contrast Enhanced CTA of the Chest	X						X		
RV/LV Diameter Ratio with each CTA	X						X		
Eligibility Criteria	X	X							
Anticoagulation ³	X	X	X	X	X				
Ultrasound Guided Access			X						
IR / Cath Lab: Invasive Hemodynamic Data ⁴			X						
IR / Cath Lab: r-tPA Pulse Sprays Administration			X						
Bashir™ Endovascular Catheter(s) and r-tPA Use ⁵		X	X	X					
ICU: PAS / PAD / Mean PA from Sheath(s)					X				
ICU: Mixed venous S _v O ₂ from Sheath					X				
r-tPA Infusion			X	X					
CO/CI by Modified Fick Method			X		X				
Medications (antiplatelet, anticoagulant, cardiac meds, and NSAIDs)	X	X	X	X	X	X	X ⁶	X	X
AEs / SAEs		X	X	X	X	X	X ⁶	X	X
Contrast Enhanced Chest CTs to Core Lab	X					X			
COVID-19 Site Impact Assessment Form ⁷									

¹ INR is only required at baseline for patients on Coumadin (warfarin) and must be ≤ 1.5 prior to enrollment. If patient is eligible for the study, Coumadin will be discontinued temporarily for study purposes.

² Pre-procedure suggested aPTT be maintained at therapeutic dose. Suggested aPTT during r-tPA administration decrease dose of UFH to 5-8 units/kg/hr up to a maximum of 1,000 units/hr.

³ Refer to protocol section 7.1.4.

[figure not shown]
⁴ Required: PAS, PAD, PA Mean, CO, CI, S_pO₂, S_vO₂ / at baseline, & post-infusion in the ICU. Swan-Ganz or angled pigtail may be used. CO= Modified Fick calculation.

⁵ IV solution must be mixed according to protocol and infuse at the prescribed rate into target PA, or both PAs if bilateral PE. Infusion is to be administered over approximately 5 hours.

⁶ If a study subject is discharged from the hospital prior to the 72-hour visit, a telephone follow-up in lieu of F2F follow-up will be conducted to verify that an AE and/or a change in medication has not occurred. If either of these have occurred, additional detail will be collected over the phone and documented.

⁷ If the study subject is unable to attend the visit in person, or in the event any study required test is omitted due to COVID-19, a protocol deviation form will be completed.

APPENDIX 25.2 RESCUE STUDY ANTICOAGULATION SCENARIOS

APPENDIX 25.3 INFORMED CONSENT FORM

(The informed consent form is an appendix to the protocol and is provided separately in MS Word® format for site to edit according to IRB requirements)

APPENDIX 25.4 CASE REPORT FORM

(The case report form is an appendix to the protocol and is provided separately as a template for the electronic data capture database)

APPENDIX 25.5 CORE LAB PROTOCOLS

(The core lab protocols are an appendix to the protocol and is provided separately.)

APPENDIX 25.6 COVID-19 CONTINGENCY PLAN

STEP 1 Evaluate Impact to the Study

The Impact Assessment Form will be completed by each site and submitted to the CRO representative. The investigational site operations will be evaluated to determine impact of the COVID-19 Pandemic. The Impact Assessment Form will be reviewed with the sponsor.

STEP 2 Alternate Study Plans

The CRO representative will review the Impact Assessment Form with the sponsor and will contact the site to confirm the site's proposed appropriate alternative plan under the following conditions:

1. Patient enrollment activities cannot be conducted in full compliance with the current protocol.

If the impact affects the ability to complete any of the required activities for study enrollment, the site will not be activated, or enrollment will be suspended if the site was previously activated, until full operations can be restored. A Suspension of Study Due to COVID-19 Notice will be issued to the site. The investigator will submit the notice to the participating IRB.

2. Patient follow-up cannot be conducted in full compliance with the current protocol.

If the impact affects the follow-up visits for patients who have already been enrolled and treated with the study device, follow-up should be completed according to the protocol if possible. The Impact Assessment Form will be completed and submitted to the CRO representative. Based on the information given in the Impact Assessment Form, a follow-up plan for the site should be provided by the site on the Impact Assessment Form to the CRO. Additionally, the investigator will submit the completed Impact Assessment Form to the participating IRB.

STEP 3 Restoration of Clinical Research Operations**1. Resuming Clinical Research Operations**

As soon as the site can confirm that clinical research operations have resumed, or a due date is defined for resumption, the site will notify the CRO representative.

2. Activation Letter

The CRO, with approval from the study sponsor, will issue an Activation Letter or Addendum to the Suspension of Study Due to COVID-19 Notice with an effective date. This will restore the site to resume active status and return to all activities as defined per the protocol.

RESCUE STUDY COVID-19 SITE IMPACT ASSESSMENT FORM

SECTION 1 GENERAL IMPACT ASSESSMENT- ANSWER ALL QUESTIONS		
Site Name:		Site Number:
Investigator Name:		
Are any enrollment activities per the study protocol impacted?		 No  Yes If yes, site may not be activated, or new enrollment may be suspended until full operation can be restored.
Are any follow-up activities per the protocol impacted?		 No  Yes If yes, complete section 2 below
Are monitoring activities impacted?		 No  Yes If yes, complete section 3 below
Are any enrolled subjects impacted?		 No  Yes If yes, complete section 4 below
Record an effective date when full operations will resume:  N/A		____ / ____ /20____ (mm/dd/yyyy)
Comments:		
SECTION 2 IMPACT ON FOLLOW-UP ASSESSMENTS – ANSWER ALL QUESTIONS		
Describe what follow-up assessments are impacted or cannot be conducted and if there is an alternate method to utilize (i.e. telephone, video conference or other)		
Assessment	Affected?	If YES, Explain Alternate Modified Plan
24 Hours Post r-tPA Completion	 No  Yes  N/A	
48 Hours Post r-tPA Completion	 No  Yes  N/A	
72 Hours Post r-tPA Initiated	 No  Yes  N/A	
Hospital Discharge	 No  Yes  N/A	
30-Day Follow-up	 No  Yes  N/A	

Site Name:			Site Number:
Assessment		Affected?	If YES, Explain Alternate Modified Plan
Concomitant Medications		 No  Yes  N/A	
AE/SAE/UADE		 No  Yes  N/A	
SECTION 3 IMPACT ON DATA MONITORING – ANSWER ALL QUESTIONS			
Assessment		Affected?	If YES, Explain Impact / Limitations
Are there any impacts affecting monitoring at the site? (Obtaining access to the source documentation)		 No  Yes	
Has a remote monitoring plan been implemented at the site as an alternative to on-site monitoring?		 No  Yes	
SECTION 4 LIST OF ENROLLED SUBJECTS IMPACTED			
Subject #	Plan		
Person Completing Form Printed Name:		Signature & Date:	____/____/20____
Physician Printed Name:		Signature & Date:	____/____/20____

